11. MANAGEMENT AND REPORTING OF ADVERSE EVENTS/ADVERSE REACTIONS

Requirements

Table 6 summarizes the requirements for recording safety events on the CRF and for reporting safety events to the Pfizer Drug Safety Unit (DSU) on the Non-Interventional Study Adverse Event Report Form for Protocols with Stipulated Active Collection of Adverse Events herein after referred to as the NIS AEM Report Form.

These requirements are delineated for 5 types of safety events: (1) serious AEs (SAEs); (2) non-serious AEs (as applicable); and scenarios involving: (3) exposure during breast feeding, medication error, overdose, misuse, extravasation, lack of efficacy; (4) exposure during pregnancy (EDP), and (5) occupational/environmental exposure. These events are defined in the section "Definitions of safety events".

Table 6. Safety Event Reporting Requirements

Safety event	Recorded on the CRF	Reported on the NIS AEM Report Form to Pfizer Safety within 24 hours of awareness
SAE ^a	All	All
Non-serious AE ^a	All	All
Scenarios involving exposure during breastfeeding, medication error, overdose, misuse, extravasation, lack of efficacy	All (regardless of whether associated with an AE/SAE)	All (regardless of whether associated with an AE/SAE) Note: Any associated AE/SAE is reported together with the exposure scenario.
Scenarios involving EDP	All (regardless of whether associated with an AE/SAE)	All (regardless of whether associated with an AE/SAE)
Scenarios involving occupational/environmental exposure	Not applicable	All (regardless of whether associated with an AE/SAE)

AE = adverse event; AEM = adverse event monitoring; EDP = exposure to a drug during pregnancy; NIS = non-interventional study; SAE = serious adverse event

For each safety event, the investigator must pursue and obtain information adequate both to determine the outcome of the AE and to assess whether it meets the criteria for classification as an SAE (refer to section "Serious Adverse Events" below).

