Hospitalization is defined as any initial admission (even if less than 24 hours) to a hospital or equivalent healthcare facility or any prolongation to an existing admission. Admission also includes transfer within the hospital to an acute/intensive care unit (eg, from the psychiatric wing to a medical floor, medical floor to a coronary care unit, neurological floor to a tuberculosis unit). An emergency room visit does not necessarily constitute a hospitalization; however, an event leading to an emergency room visit should be assessed for medical importance.

Hospitalization in the absence of a medical AE is not in itself an AE and is not reportable. For example, the following reports of hospitalization without a medical AE are not to be reported:

- Social admission (eg, patient has no place to sleep)
- Administrative admission (eg, for yearly exam)
- Optional admission not associated with a precipitating medical AE (eg, for elective cosmetic surgery)

PFIZER CONFIDENTIAL

- Hospitalization for observation without a medical AE
- Admission for treatment of a pre-existing condition not associated with the development of a new AE or with a worsening of the pre-existing condition (eg, for work-up of persistent pre treatment lab abnormality)

Causality assessment

The investigator is required to assess and record the causal relationship.

An investigator's causality assessment is the determination of whether there exists a reasonable possibility that lorlatinib caused or contributed to the safety event. For all safety events, sufficient information should be obtained by the investigator to determine the causality.

If the investigator's final determination of causality is "unknown" and s/he cannot determine whether lorlatinib caused the event, the safety event must be reported per the process outlined in Table 6.

If the investigator cannot determine the etiology of the event but s/he determines that lorlatinib did not cause the event, this should be clearly documented on the CRF and the NIS AEM Report Form.

Endpoint Adjudication Committee

Not applicable

Exposure During Pregnancy, Exposure During Breastfeeding, Environmental Exposure and Occupational Exposure

Exposure during pregnancy

Prospective and retrospective exposure during pregnancy (EDP) reports are reportable using the NIS AEM Report Form and the EDP Supplemental Form, irrespective of the presence of an associated safety event.

The procedures for reporting as per Table 6 should be followed.

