If the mother or the fetus experience a safety event during administration of such drugs, the safety event must be reported without the event EDP reported.

An EDP occurs if:

- A female participant becomes, or is found to be, pregnant either while receiving or having been exposed to lorlatinib, or the female becomes, or is found to be, pregnant after discontinuing and/or being exposed to lorlatinib (maternal exposure).
- A male participant who is receiving or has discontinued lorlatinib inseminates a female partner prior to or around the time of conception and/or during the partner pregnancy.
 - In this case, the study participant will be provided with the Pregnant Partner Release of Information Form to deliver to their partner. It must be documented that the study participant was given this letter to provide to their partner.

All reports submitted should include the anticipated date of delivery, as applicable, and should be managed as follows:

- Follow-up is conducted to obtain general information on the pregnancy; in addition, followup is conducted to obtain information on EDP outcome for all EDP reports with pregnancy outcome unknown.
- A pregnancy is followed until completion or until pregnancy termination (eg, induced abortion) and Pfizer is notified of the outcome. This information is provided as a followup to the initial EDP report.
- In the case of a live birth, the structural integrity of the neonate can be assessed at the time of birth.
- In the event of a termination, the reason(s) for termination should be specified and, if clinically possible, the structural integrity of the terminated fetus should be assessed by gross visual inspection (unless pre-procedure test findings are conclusive for a congenital anomaly and the findings are reported).
- If the outcome of the pregnancy meets the criteria for an SAE (eg, ectopic pregnancy, spontaneous abortion, intrauterine fetal demise, neonatal death, or congenital anomaly [in a live born, a terminated fetus, an intrauterine fetal demise, or a neonatal death]), the procedures for reporting SAEs should be followed.

Additional information about pregnancy outcomes that are reported as SAEs:

- Spontaneous abortion includes miscarriage and missed abortion
- Neonatal deaths that occur within 1 month of birth should be reported, without regard to
 causality, as SAEs. In addition, infant deaths after 1 month should be reported as SAEs

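### One sentence in Section 11 tells sites to report a maternal or fetal safety event without the pregnancy exposure, contradicting Table 6 and the opening of the same subsection

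*Protocol*

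**What the plan says.** Three places in Protocol Section 11 bear on the point.

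- **Table 6, row for EDP scenarios.** Under both the CRF column and the column for the NIS AEM Report Form (within 24 hours of awareness), the entry is "All (regardless of whether associated with an AE/SAE").
- **Exposure during pregnancy, opening.** Prospective and retrospective EDP reports "are reportable using the NIS AEM Report Form and the EDP Supplemental Form, irrespective of the presence of an associated safety event". The subsection then defers to the table: "The procedures for reporting as per Table 6 should be followed".
- **Exposure during pregnancy, next sentence.** For a safety event arising in mother or fetus while the drugs in question are being taken, "the safety event must be reported without the event EDP reported".

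The same subsection ties two later steps to an EDP report. On outcome, "followup is conducted to obtain information on EDP outcome for all EDP reports with pregnancy outcome unknown". On completion or termination of the pregnancy, the sponsor is notified, and "This information is provided as a followup to the initial EDP report".

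**The concern.** The third instruction appears to reverse the first two in exactly the situation where both matter: an exposed pregnancy in which something has gone wrong. It is worded as an obligation, and it comes straight after the line sending the site to Table 6. A coordinator reading down the page would take it as the specific rule for that case.

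At stake is whether such an exposure reaches the sponsor's safety unit identified as a pregnancy exposure, with its Supplemental Form, or only as an ordinary AE or SAE. The study is a designated post-authorisation safety study, its primary objective is safety, and EDP scenarios are among the variables listed in the abstract. Two conflicting instructions on 24-hour reporting should not stand in the operative text.

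**Working it through.** No formula applies. The check sets the instructions side by side and traces what depends on each.

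**Step 1. Apply each rule to the two possible cases.**

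| Case | Table 6, EDP row | Opening of the pregnancy subsection | The disputed sentence |
|---|---|---|---|
| Exposed pregnancy, no safety event | Record on CRF; report within 24 hours | Report on NIS AEM Report Form and EDP Supplemental Form | Does not apply |
| Exposed pregnancy, safety event in mother or fetus | Same | Same | Report the safety event without the EDP |

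The rules agree in the first row and conflict in the second. The opening rule expressly covers the second row, since it holds "irrespective of the presence of an associated safety event".

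**Step 2. Look for an exemption that would reconcile them.** The disputed sentence refers to administration of certain drugs, in the plural, but nothing before it in the subsection identifies any. Lorlatinib is the only drug under discussion, and Section 11 exempts no class of drug from EDP reporting. As written, the sentence applies to lorlatinib.

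**Step 3. Trace what hangs on the EDP report.** Three things do:

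- the EDP Supplemental Form, which the subsection opening attaches to EDP reports;
- the follow-up of unknown outcomes, which is written for EDP reports;
- the filing of the pregnancy outcome, which is a follow-up to the initial EDP report.

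If that report is not made, the second has no report to start from and the third has none to attach to.

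**Step 4. Trace what does not hang on it.**

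- CRF recording of the EDP. Table 6 has a separate CRF column, and the disputed sentence speaks only of reporting.
- Reporting of the safety event itself. Table 6 requires all serious and non-serious AEs within 24 hours of awareness, and the Requirements text has them followed until they resolve or stabilise.
- Pregnancy outcomes meeting SAE criteria. Ectopic pregnancy, spontaneous abortion, fetal demise, neonatal death and congenital anomaly go through the SAE procedures.
- Following the pregnancy to completion or termination, which the subsection states without restriction.
- The anticipated delivery date, which is asked for on all submitted reports, as applicable.

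**Step 5. Size.** The planned sample is 116 patients. The protocol gives no pregnancy rate, so no count of affected cases can be derived.

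**The case against.** The strongest answer is that the sentence is stray wording with an uncertain meaning, and that little would be lost even if it were obeyed. The line before it points to Table 6. The phrase about the drugs has no antecedent. The reference to the event EDP might mean only the event term entered on the form, since the Medication error subsection lists an event term as one element of a report. On that reading the sentence is about coding and does not cancel the exposure report.

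Part of this stands. The meaning is uncertain, and it is not established that reports would be lost. But the sentence does not say that it concerns coding, and a reader cannot recover that intent from the page. If coding was meant, the sentence still needs rewriting.

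Three stronger conclusions might be drawn, and the documents support none of them.

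- **That exposures with harm lose their outcome follow-up altogether.** The protocol follows a pregnancy to completion without restriction, follows each safety event until it resolves or stabilises, and keeps the SAE route for serious outcomes. What is at risk is the EDP report, its form and the steps worded for EDP reports.
- **That the study's EDP data would be selectively short of cases with an event.** Study data come from the e-CRF (Sections 9.4 and 9.6), and the CRF requirement in Table 6 is untouched.
- **That nearly every maternal exposure would trigger the sentence, because all lorlatinib patients in CROWN had an AE.** That figure accumulated over a median treatment duration of 57.0 months (Section 7). The relevant window is administration during an exposed pregnancy, which may be brief.

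**Conclusion.** The contradiction holds. For an exposed pregnancy with a maternal or fetal safety event, one sentence in Section 11 conflicts with Table 6 and with the opening of its own subsection, and nothing in the document resolves it. The consequence is conditional: a site that takes the sentence literally could omit the EDP report and its Supplemental Form, leaving the pregnancy outcome with no initial EDP report to join.

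The size is small and cannot be quantified. Such cases should be rare. The safety event, the SAE-level outcomes and the CRF entry for the exposure all remain required. No objective, endpoint, sample size or analysis changes. The conclusion rests on reading the sentence as applying to lorlatinib, the only drug the section discusses. It is worth correcting because it concerns mandatory safety reporting in a safety study and the remedy is slight.

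**What to change.** Either delete the sentence, or reconcile it with Table 6 and the subsection opening. Suggested wording for the second option: *If the mother or fetus has a safety event, that event is reported in addition to the EDP. The EDP is still reported on the NIS AEM Report Form and the EDP Supplemental Form, within the timeline in Table 6.*

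The sources of this wording should be kept straight. The Supplemental Form comes from the opening of the pregnancy subsection; Table 6 does not mention it. Table 6 supplies the duty to report and the 24-hour timeline. Its note that an associated AE or SAE is reported together with the exposure belongs to the row for breastfeeding, medication error and similar scenarios, so it should not be cited as an existing rule for EDP.

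The cost is one sentence in Section 11 and a line in site training. No data collection form or analysis needs to change.

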11.1. Single Reference Safety Document

The SmPC/data sheet of lorlatinib will serve as the single reference safety document during the course of the study, which will be used by Pfizer safety to assess any safety events reported to Pfizer Safety by the investigator during the course of this study.

The single reference safety document should be used by the investigator for prescribing purposes and guidance.

12. PLANS FOR DISSEMINATING AND COMMUNICATING STUDY RESULTS

Results from interim analyses and final analyses, including subgroup analyses or particular research questions to be further specified in the statistical analysis plan, will be submitted to national or international conferences and/or full-paper publications. Final study results will be filed in Pfizer's Global Document Management System upon final study completion. The final report will be placed at the disposal of the competent higher regional authority within one year after its completion.

In the event of any prohibition or restriction imposed (eg, clinical hold) by an applicable competent authority in any area of the world, or if the investigator is aware of any new information which might influence the evaluation of the benefits and risks of a Pfizer product, Pfizer should be informed immediately.

In addition, the investigator will inform Pfizer immediately of any urgent safety measures taken by the investigator to protect the study patients against any immediate hazard, and of any serious breaches of this NI study protocol that the investigator becomes aware of.

15. LIST OF FIGURES

None

16. ANNEX 1. LIST OF STAND ALONE DOCUMENTS

None

